14 DATA SAFETY MONITORING

The Cystic Fibrosis Foundation Data Safety Monitoring Board (DSMB) will establish a Data Monitoring Committee (DMC) to review data relating to safety and efficacy, to conduct and review interim analyses, and to ensure the continued scientific validity and merit of the study, according to the Cystic Fibrosis Foundation Data Safety Monitoring Board Operations Manual and a DMC Charter to be established for this protocol. There will be 3 interim review(s) conducted by the DMC for the purpose of monitoring study conduct and assessing subject safety. Enrollment for subsequent cohorts will not begin until after the DMC reviews the data for the current cohort and approves proceeding to the next cohort. Further details regarding the timing and content of the interim reviews is included in the statistical section below.

15 STATISTICAL METHODS AND CONSIDERATIONS (BASED UPON PRIMARY AND SECONDARY ENDPOINTS)

Prior to the analysis of the final study data, a detailed Statistical Analysis Plan (SAP) will be written describing all analyses that will be performed. The SAP will contain any modifications to the analysis plan described below.

15.1 Data Sets Analyzed

All eligible subjects who are enrolled into the study and receive at least one dose of the investigational product (the Safety Population) will be included in the safety analysis. The analyses will be conducted on all data available. Subjects with missing data for a particular analysis will not be included as applicable.

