4 STUDY DESIGN

4.1 Study Overview

Overview of Study Design. A prospective, single-center, single-dose, dose-escalation, open-label interventional study to evaluate the safety and tolerability of allogeneic hMSCs in 15 clinically stable adult subjects with CF. Because the subject's own cells will contain two CFTR mutations, allogeneic hMSC infusion is being employed in this study. Screening data will be reviewed to determine subject eligibility. Subjects who meet all inclusion criteria and none of the exclusion criteria will be entered into the study. The Tables in Appendix II review the schedule of study visits. After a two to six week screening period, subjects will have the Baseline visit (Days 1-2) where they will undergo a single infusion of up to 5×10^6 allogeneic hMSCs/kg. The CCC and NCRM at Case Western Reserve University have a long-standing approach to identifying, screening and using donors to provide hMSCs. Donors are screened per FDA guidelines for cells and tissues (21 CFR 1271). The FDA guidelines are similar to those used for blood donation by Red Cross. The allogeneic hMSCs used in this study will come from one or two healthy donors who have been well-characterized by the CCC and whose sera test negative for CMV antibodies. Healthy donors will be followed by the PI or designee for any procedure-related AEs. Infusions will be performed in the Dahms Clinical Research Unit at University Hospitals Cleveland Medical Center. Study participants will be monitored for the development of infusion-related toxicities for 24 hours. Subjects will have subsequent study visits on Days 7, 14, 28, Months 3 and 6 and telephone calls on Days 4 (or 5), 21, 56 and Month 12. Subject safety and tolerability of the single dose of hMSCs will be evaluated at the study visits by reviewing subject diaries, interval histories, and subject questionnaires, performing physical examinations and spirometry, and obtaining safety laboratories. In addition to infusion related toxicities, special focus will also be placed upon detecting pulmonary exacerbations since an anti-inflammatory therapy theoretically could suppress the immune system to the point where it leads to increased infectious complications. Appendix I lists the criteria for a pulmonary exacerbation. This study will also explore efficacy endpoints that previously have been shown to be key regulators in CF and/or hMSCs: Serum inflammatory biomarkers (calprotectin, MPO, GM-CSF, IL-1 β , IL-6, IL8, IL-17, and TNF- α), and sputum inflammatory biomarkers (white cell counts with differentials, IL-1 β , IL-6, IL-8, IL-10, IL-17, GM-CSF, MIP-3 α , TNF- α , and active proteases including neutrophil elastase, α_1 -anti-trypsin, and MMP-9). These studies will be repeated on Days 7 and 28 and compared to Baseline values (with-in subject comparison). All subject samples will be archived for future studies to explore the impact on the microbiome and for future translational projects. Finally, an optional diagnostic bone marrow exam will be performed between screening and Day 1 on CF subjects willing to undergo the procedure, banked, and used for future translational studies.

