
The following treatment regimens will be used:

- Experimental treatment hMSCs at the following doses: 1×10^6 , 3×10^6 or 5×10^6 hMSCs/kg body weight

All subjects who begin an infusion of the investigational product will be considered evaluable for safety and efficacy analyses. Incidence of AEs will be monitored during the trial.

Safety assessments will be based on the incidence of AEs including protocol defined pulmonary exacerbations and changes in lung function, sputum microbiology, safety labs, subject questionnaire, and physical examination. An Acute Illness Visit will be arranged for any subject who experiences any abrupt change in baseline clinical status, between Visit 2 and Visit 5 (the 28 days following infusion) that in the estimation of an investigator, research coordinator, other health care provider or the subject necessitates an in-person office visit.

Total duration of subject participation in the study will be approximately 13 months. Long-term post-treatment follow-up will continue for 12 months after the infusion of the investigational product for each subject. Data on subject survival and on the occurrence of new health problems will be collected from all subjects who receive the investigational product infusion. The information will be gathered during a study visit, a routine clinic visit or via telephone. These data will be collected in the source documents (e.g., subject medical record) and transcribed into an electronic CRF. Any unsuccessful efforts to contact the subject (e.g., dates of unanswered phone calls, failure to show for a clinic visit, etc.) will be documented in the subject's source documents.

Total duration of conducting the study is expected to be approximately 24 months.

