6.3 Exclusion Criteria

1. Use of an investigational agent within the 4-week period prior to Visit 1 (Day -42 to -10)
2. Chronic daily (>10 mg) or alternate daily (>20 mg on alternate days) use of systemic corticosteroids within the 4 weeks prior to Visit 1 (Day -42 to -10) or initiation of any dosage of systemic corticosteroids within 72 hours prior to Visit 2 (Day 1)
3. Use of hydroxychloroquine or immunosuppressants
4. Initiation of a new antibiotic (oral, IV, and/or inhaled) that is not part of the subject's maintenance regimen for treatment of acute respiratory symptoms within 2 weeks prior to screening through Visit 2 (Day 1)
5. Initiation of any new chronic therapy (e.g., Pulmozyme[®], hypertonic saline, Kalydeco[®], Orkambi[®], high-dose ibuprofen azithromycin, TOBI[®], Cayston[®], nebulized colistin, bronchodilators, inhaled corticosteroids, etc.) within 4 weeks prior to screening
6. Active treatment for non-tuberculous *Mycobacteria*
7. History of a sputum culture positive for a *Burkholderia cepacia* complex organism in the previous 12 months
8. Current tobacco smoker
9. Oxygen saturation $< 92\%$ on room air at Visit 1 (Day -42 to -10)
10. History of pulmonary hypertension
11. SGOT (ALT) or SGPT (AST) > 2.5 times the upper limit of normal at screening, documented biliary cirrhosis, or portal hypertension
12. Total bilirubin concentration >1.2 mg/dL at screening
13. Creatinine > 1.8 mg/dL at screening
14. Pregnant, breastfeeding, or unwilling to practice birth control between Visit 2 (Day 1) and Telephone Call 3 (Day 56) (acceptable forms of contraception: abstinence, hormonal birth control, intrauterine device, or barrier method plus a spermicidal agent), unless surgically sterilized or postmenopausal
15. Screening hematology with white blood cell count $< 4.5 \times 10^9$ cells/L, hematocrit $< 30\%$, and platelets $< 150 \times 10^9$ platelets/L
16. History of invasive cancer requiring systemic therapy
17. History of organ transplantation
18. Currently listed for lung transplantation or having potential to be listed for lung transplantation in the succeeding 12 calendar months from screening
19. Subject unlikely to complete the study as determined by the Investigator

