7 CONCURRENT MEDICATIONS

All subjects should be maintained on the same medications from screening through Visit 5 (Day 28), as medically feasible, with no introduction of new chronic therapies. Medication history will be collected for all drugs for the 30 days prior to screening. If any changes in concomitant medications are required due to AEs (i.e. illness, laboratory abnormalities, surgical procedures, etc.), the reason(s) for the change(s) must be documented. Subjects who require treatment for a pulmonary exacerbation during the course of the trial will remain in the study.

Subjects who have routinely taken more than 10 mg/day (or >20 mg on alternate days) of prednisone or other systemic corticosteroids 4 weeks prior to Visit 1 (Day -42 to -10) or who have taken these medications as needed within 72 hours prior to Visit 1 or 2 will be excluded from participation. Subjects may be re-screened once. For those subjects taking alternate month TOBI® or Cayston® therapy, on/off cycles must be timed such that a subject is at the same phase of a cycle at Visits 2, 3, 4, and 5.

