10.4 Visit 2 (Baseline Visit: Day 1)

1. Perform and record RSSQ prior to any other study procedures
2. Administer and review CFRSD prior to any other study procedures and record any AEs that occurred since Visit 1
3. Review and record interval history
4. Review and record any changes to concomitant medications
5. Review inclusion/exclusion criteria
6. Measure and record weight without shoes
7. Perform and record vital signs, including a blood pressure after the subject has been seated for 5 minutes
8. Perform and record oximetry
9. Collect blood for clinical laboratory tests (comprehensive chemistry panel, ESR, hs-CRP, complete blood count with differential, direct bilirubin and LDH) and vitamin D
10. Collect blood for inflammatory mediators (calprotectin, MPO, GM-CSF, IL-1 β , IL-6, IL-8, IL-17, and TNF- α)
11. Collect urine for clinical laboratory test (urinalysis)
12. Collect urine for pregnancy test prior to infusion
13. Administer 3 puffs of albuterol 15 minutes prior to spirometry if subject is likely to require induction to obtain sputum during the visit
14. Perform and record spirometry approximately 2 hours before hMSC infusion
15. Obtain sputum for clinical laboratory tests (quantitative culture and microbiology) and for research tests (cell count with differential, IL-1 β , IL-6, IL-8, IL-10, IL-17, GM-CSF, MIP-3 α , TNF- α , neutrophil elastase, α_1 -anti-trypsin, and MMP-9). Subjects will be asked to provide sputum via spontaneous expectoration. If a subject is unable to provide sputum spontaneously, then the subject may undergo sputum induction according to the current TDN SOP. Any AEs related to the sputum procedure will be recorded.
16. Temperature, blood pressure, heart rate, respiratory rate and oxygen-saturation are measured prior to the infusion. Subjects should be seated for 5 minutes prior to obtaining vital signs.
17. Perform a complete physical examination
18. Infusion of hMSCs
19. Temperature, blood pressure, heart rate, respiratory rate and oxygen-saturation are measured prior to infusion and at 10 (\pm 5), 20 (\pm 5), 30 (\pm 5), 60 (\pm 15), and 90 (\pm 15) minutes and 2 hours (\pm 15 minutes) and 4 hours (\pm 15 minutes) post-infusion completion and then every 4 (\pm 15 minutes) hours for the remainder of the 24-hour observation period. Subjects should be seated or lying down for 5 minutes prior to obtaining vital signs.

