13 PROTOCOL VIOLATIONS

A protocol violation occurs when the subject or investigator, fails to adhere to significant protocol requirements affecting the inclusion, exclusion, subject safety and primary endpoint criteria. Protocol Violations for this study include, but are not limited to, the following:

- Failure to meet inclusion/exclusion criteria
- Use of a prohibited concomitant medication

Failure of the investigators or study staff to comply with Good Clinical Practice (GCP) guidelines will also result in a protocol violation. The medical monitor will determine if a protocol violation will result in withdrawal of a subject. When a protocol violation occurs, it will be discussed with the investigator and a Protocol Violation Form detailing the violation will be generated. This form will be signed by the Investigator. A copy of the form will be filed in the site's regulatory binder.

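### Section 15.1 limits the Safety Population to eligible subjects, while section 4.1 counts everyone who begins an infusion; the two disagree for an infused subject later found ineligible

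*Combined protocol and SAP*

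**What the plan says.** Two sections say who counts for safety.

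- Section 15.1: "All eligible subjects who are enrolled into the study and receive at least one dose of the investigational product (the Safety Population" form the set for the safety analysis. The next sentence adds: "The analyses will be conducted on all data available".
- Section 4.1: "All subjects who begin an infusion of the investigational product will be considered evaluable for safety and efficacy analyses".

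Three other places bear on whether an ineligible subject can be infused.

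- Section 4.1, on entry: "Subjects who meet all inclusion criteria and none of the exclusion criteria will be entered into the study".
- Section 10.4 repeats the check on Day 1 before the infusion: "Review inclusion/exclusion criteria".
- Section 13 names, first in its list of protocol violations, "Failure to meet inclusion/exclusion criteria". It leaves to the medical monitor whether the subject is withdrawn, and gives no rule for the analysis set.

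Section 15.3 reports AEs and SAEs by dose cohort as counts and percentages, for all grades and for grade 3 and above, and compares cohorts with Fisher's exact test. The opening of section 15 leaves a detailed SAP to be written before the final analysis.

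**The concern.** A safety set normally follows exposure. The cells have been infused whether or not an entry criterion was met, and any toxicity in that subject is information about the product. With *eligible* as a condition, a subject found after the infusion to have failed a criterion drops out of the tables that address the primary objective.

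Cohorts 1 to 3 have three subjects each (section 8.3.3, Table 1), so one subject is a third of a cohort's denominator. If that subject had an event, the tables lose it. If the subject had none, the rate among those left goes up. Either way, two analysts following two sections of the same protocol would produce different tables from the same data.

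**Working it through.** **Step 1. The two definitions side by side.**

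| Condition | Section 4.1 | Section 15.1 |
|---|---|---|
| Met all entry criteria | not required | required |
| Exposure | infusion begun | at least one dose received |
| Infused, later found ineligible | in | out, as worded |

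The exposure row matters only for a stopped infusion. Section 8.5 has staff record the part given as the dose administered, which favours inclusion under 15.1 too. The eligibility row is the real difference.

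**Step 2. Can the case arise?** The entry rule in 4.1 and the Day 1 recheck in 10.4 make it uncommon. They cannot exclude it, because a recheck does not catch facts learned after the infusion, and section 13 lists the violation. The documents give no frequency, so none is assumed.

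**Step 3. Does anything else in 15.1 settle it?** The sentence on using all available data follows the population definition. It concerns the data of subjects in the set and does not widen the set.

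**Step 4. What depends on the set?** The 15.3 summaries and the Fisher's exact comparison do. AE capture (5.1, 9.1.11), SAE documentation (11.2.1), DMC review of each cohort (14) and the DLT rule (8.1) carry no eligibility condition.

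**Step 5. Size, as an illustration.** The documents state no figure to reproduce. Inputs: cohorts of 3, 3, 3 and 6 (Table 1), and 3 + 3 + 3 + 6 = 15 (section 15.6). Assumption: exactly one infused subject is later found ineligible. Exact (Clopper-Pearson) 95% limits for x events in n are

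- lower = Beta quantile 0.025 with parameters (x, n − x + 1), or 0 if x = 0;
- upper = Beta quantile 0.975 with parameters (x + 1, n − x), which for x = 0 is 1 − 0.025^(1/n).

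For example, 0/2 gives 1 − 0.025^(1/2) = 84.2%, and 0/3 gives 1 − 0.025^(1/3) = 70.8%.

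If the omitted subject had the only grade 3 or higher AE:

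| Group | Under 4.1 | Under 15.1 |
|---|---|---|
| Three-subject cohort, not replaced | 1/3 = 33.3% (0.8 to 90.6%) | 0/2 = 0% (0 to 84.2%) |
| Three-subject cohort, withdrawn before Visit 5 and replaced | 1/4 = 25% (0.6 to 80.6%) | 0/3 = 0% (0 to 70.8%) |
| Six-subject cohort 4, not replaced | 1/6 = 16.7% (0.4 to 64.1%) | 0/5 = 0% (0 to 52.2%) |
| All 15, not replaced | 1/15 = 6.7% (0.2 to 31.9%) | 0/14 = 0% (0 to 23.2%) |

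The replacement row follows from sections 6.1 and 12.1, which replace subjects who withdraw before Visit 5, and from section 13, under which the medical monitor may withdraw a violator.

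If the omitted subject had no such event and one other subject did, and nobody was replaced, a three-subject cohort goes from 1/3 to 1/2 (50%, 1.3 to 98.7%), and the whole trial from 1/15 to 1/14 (7.1%, 0.2 to 33.9%).

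Section 15.3 does not plan confidence intervals. They are shown here only to indicate how little these denominators can bear.

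**The case against.** The best reply is that *eligible* in 15.1 is merely descriptive. Section 4.1 admits only subjects who meet the criteria, 6.1 and 8.1 use the word in that ordinary sense, and 15.1 contains no rule that removes anyone. Section 4.1 states the broader rule without qualification, and the SAP is still to come. This reduces the likelihood of harm but does not remove the conflict. The word stands inside the definition of a named population, section 13 foresees subjects for whom it is not redundant, and nothing says that 4.1 prevails. If the word is redundant, deleting it loses nothing.

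A second reply is that no toxicity would be lost to the trial. That stands. A reader might infer from 15.1 that an ineligible subject's event would disappear, or that it could change dose escalation. The documents do not support either: events are still captured, graded and reported, the DMC still reviews the cohort, and the DLT rule in 8.1 does not refer to the Safety Population. The event would be missing only from the 15.3 summaries and comparison.

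A reader might also take the corticosteroid wording as a ready route to such a subject. Section 6.3 excludes "initiation of any dosage of systemic corticosteroids within 72 hours prior to Visit 2 (Day 1"), whereas section 7 says that subjects "who have taken these medications as needed within 72 hours prior to Visit 1 or 2 will be excluded from participation". The mismatch is real. But 6.1 ties eligibility to the inclusion and exclusion criteria, so a subject who passes 6.3 is arguably eligible for 15.1 whatever section 7 says. It is a separate inconsistency and is not needed for this point.

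**Conclusion.** The point holds as an inconsistency between 15.1 and 4.1 over one kind of subject: infused, then found ineligible. Read literally, 15.1 drops an exposed subject from the primary safety summaries. The probability is low and cannot be put in figures from the documents. Given that it happens, and that the subject had the only severe event, a three-subject cohort would be reported with no severe event instead of 1/3 (or instead of 1/4 after replacement), and the whole trial as 0/14 instead of 1/15.

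These figures assume one such subject and one such event; they are not a forecast. The conclusion rests on the wording alone and does not extend to dose escalation, DLT counting or safety reporting. It should be fixed because it touches the primary safety tables and the remedy is small.

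**What to change.** In 15.1, delete *eligible* and define the Safety Population as all subjects in whom an infusion was started, regardless of eligibility or of the amount received. This agrees with 4.1 and also settles the stopped-infusion wording. Flag subjects with an eligibility violation in a listing. If an eligibility-restricted analysis is wanted, give it a separate, named population. Carry the same definition into the SAP.

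The cost is one sentence and one listing, with no added visits, procedures or subjects. A change to the protocol text goes through the IRB route in section 17.2. The downside is that the safety tables may include a subject who did not meet an entry criterion; the listing makes that visible.

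Separately, the 72-hour corticosteroid wording in 6.3 and section 7 should be reconciled.

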15.2 Demographic and Baseline Characteristics

Demographic and baseline clinical characteristics including age, gender, race, CFTR genotype, height, weight, oxygen saturation, sputum microbiology (presence of *P. aeruginosa*, methicillin-sensitive *S. aureus*, methicillin-resistant *S. aureus*, and/other Gram-negative bacteria) and pulmonary function will be reported for each subject and summarized overall using descriptive statistics such as frequency, percentage, mean or median and range. For all analyses, Baseline will be defined as the measurement prior and closest to the administration of the infusion of hMSCs.

15.3 Analysis of Primary Endpoint

The primary endpoint of this study is to determine the maximum tolerate dose among 1×10^6 hMSCs/kg, 3×10^6 hMSCs/kg, and 5×10^6 hMSCs/kg. Safety data will be analyzed at both the individual level and the dose cohort level. Safety will be evaluated using reports of adverse events (AE) and measurements of vital signs, oxygen saturation, pulmonary function, laboratory parameters and adverse events associated with procedures (sputum induction for those subjects unable to spontaneously expectorate sputum and optional bone marrow aspiration). All measurements will be reported at each time point, changes from Baseline and from the previous time point will be summarized at each time point. Premature withdrawals and reasons of withdrawals will be listed.

Clinically significant AEs and alterations in vital signs, oxygen saturation, and pulmonary function at baseline, 30 minutes, 4 hours and 24 hours after the infusion will be summarized by patient and by dose cohort using frequency/percentage and mean or median/range.

Overall AEs and SAEs in each dose cohort will be coded by body system and MedDRA classification term using frequency and percentage. Frequency and percentage of all grades and grades ≥ 3 will be reported.

AEs among dose cohorts will be compared using Fisher's exact test. All clinically significant vital sign and physical examination changes as well as laboratory test abnormalities will be presented in AE listings.

Mean or percentage of clinically significant AEs, alterations in vital signs (including decreases in systolic blood pressure ≥ 20 mmHg or diastolic blood pressure ≥ 10 mmHg), spirometry measurements (FEV₁ %, FEV₁ (Liters), FEF₂₅₋₇₅), sputum quantitative microbiology (bacterial colony forming units) and hematology, comprehensive chemistry, ESR, hs-CRP and urinalysis results measured at Baseline and at the follow-up visits will be graphically presented.

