9.1.7 Spirometry

Spirometry will be performed at all study visits and in accordance with the current American Thoracic Society recommendations for the performance and interpretation of tests. Spirometry will be obtained approximately 2 hours prior to the start of the hMSC infusion and 30 minutes, 4 hours and 24 hours after completion of the infusion. Subjects will perform spirometry as is customary for that subject at clinical visits. If the subject typically does not take albuterol prior to spirometry, then he/she will not take albuterol prior to spirometry during the study. If the subject typically takes albuterol prior to spirometry, they he/she will take albuterol prior to spirometry for this study. However there is an exception. In any subject in which it is anticipated that he/she might not be able to produce sputum spontaneously at any one of the study visits in which sputum will be obtained, then those subjects will undergo sputum induction at all visits regardless of his or her ability to spontaneously expectorate sputum at the current study visit. In these cases, those individuals will receive three inhalations of albuterol sulfate via metered dose inhaler prior to all spirometric tests obtained during the study. Approximately 15 minutes after administering albuterol sulfate, pulmonary function testing will be performed. If a study subject is unable to produce sputum at the Baseline Visit (Day 1), then sputum will not be obtained at Visits 3 (Day 7) and 5 (Day 28).

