9.1.9 Intravenous Infusion of hMSCs

Fresh MSCs are infused at Visit 2 (Day 1) from a syringe into a venous catheter followed by a saline wash. After the infusion of cells is complete, 10-ml of a normal saline flush is given immediately and a running IV of normal saline is maintained at 250 ml/hr for 4 hours. Subjects are monitored for 24 hours for infusion-related toxicity. Temperature, blood pressure, heart rate, respiratory rate and oxygen-saturation are measured prior to infusion and at 10 (\pm 5), 20 (\pm 5), 30 (\pm 5), 60 (\pm 15), and 90 (\pm 15) minutes and 2 hours (\pm 15 minutes) and 4 (\pm 15 minutes) hours post-infusion and then every 4 (\pm 15 minutes) hours for the remainder of the 24-hour observation period. Any toxicity is treated at the discretion of the managing physician, and toxicities are reported to the Principal Investigator, IRB, and FDA as appropriate.

MSC infusion has been very well tolerated. Although theoretically of concern, there have been no reported cases of immunosuppression, autoimmunity, cancer, significant lung damage, severe infection, or clinically significant ectopic tissue formation attributable to MSC infusion. MSC infusion could cause infection if the cells are contaminated. Strict aseptic technique during bone marrow aspiration, culture, thawing, and infusion and stringent microbiologic screening minimize this risk. Because of the immunosuppressive effects of MSCs, recipients potentially are at increased risk for infection.

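### The frequency summary of acute alterations in Section 15.3 uses the three spirometry times, so it leaves out 9 of the 12 post-infusion readings of vital signs and oxygen saturation

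*Combined protocol and SAP*

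**What the plan says.** **Collection.** Section 9.1.9 puts the four vital signs and saturation on one schedule. For the early period it says that "oxygen-saturation are measured prior to infusion and at 10 (\pm 5), 20 (\pm 5), 30 (\pm 5), 60 (\pm 15), and 90 (\pm 15) minutes". Two more readings follow, at 2 hours and at 4 hours, and four-hourly readings then continue "for the remainder of the 24-hour observation period". Section 10.4 and the infusion footnote to Appendix II repeat this schedule. Spirometry has its own, sparser schedule: about 2 hours before the infusion and "30 minutes, 4 hours and 24 hours after completion of the infusion" (Section 9.1.7).

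**Analysis.** Section 15.3 has three statements that bear on these readings.

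- The acute summary groups clinically significant AEs with alterations in vital signs, saturation and lung function, and says that these "at baseline, 30 minutes, 4 hours and 24 hours after the infusion will be summarized by patient and by dose cohort" using frequency and percentage, or mean or median with range.
- A general statement reads: "All measurements will be reported at each time point, changes from Baseline and from the previous time point will be summarized at each time point".
- A listing rule reads: "All clinically significant vital sign and physical examination changes as well as laboratory test abnormalities will be presented in AE listings".

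The section also tabulates all AEs and SAEs by dose cohort, without reference to reading times. Its only numeric criterion is a fall of at least 20 mmHg systolic or 10 mmHg diastolic. That criterion appears in the sentence on graphs, which concerns Baseline and the follow-up visits.

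**The concern.** The three times in the acute summary coincide with the spirometry schedule, yet the sentence also covers vital signs and saturation, which are read far more often. Read literally, a fall in saturation or blood pressure seen only at 10, 20, 60 or 90 minutes, at 2 hours, or between 8 and 20 hours has no place in the frequency by patient and by cohort.

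This matters because infusion-related safety is the primary objective (Section 3.1), and change in vital signs, including saturation, is a listed component of the primary endpoint (Section 5.1). The cells are given over 10 to 15 minutes (Section 8.3.4), and Section 1.3.6.1 names pulmonary embolism from cell clumping as a potential concern. The early readings are the densest part of the schedule, and the count uses few of them.

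**Working it through.** The plan prints no figure for this point, so there is none to reproduce. The check compares the two schedules at nominal times.

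**Step 1. Count the readings.** Section 9.1.9 gives 10, 20, 30, 60 and 90 minutes, 2 hours and 4 hours, which is 7 readings. Every 4 hours after that, to 24 hours, gives 8, 12, 16, 20 and 24 hours, which is 5. The total is 7 + 5 = 12.

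**Step 2. Compare with the acute summary.** It names 30 minutes, 4 hours and 24 hours.

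| Period | Readings scheduled | Named in the summary | Left out |
|---|---|---|---|
| First 4 hours | 7 | 2 | 5 |
| After 4 hours, to 24 hours | 5 | 1 | 4 |
| Total | 12 | 3 | 9 (9/12 = 75%) |

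**Step 3. See whether other sentences supply the count.** The general statement covers values and changes at each time. A summary at each time does not give the number of subjects affected at any time. If two subjects in a cohort of three drop at different readings, each by-time summary shows one of them. The listing has no time limit, but it is not a frequency by dose. Neither gives a worst value per subject.

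**Step 4. Gauge the effect on brief episodes.** The documents give neither duration nor onset time, so both are assumed here. Let an episode last D minutes, with onset uniform over the first W minutes after the infusion. A reading at time t falls within the episode when onset lies between t − D and t. The probability of a catch is the total length of these intervals, overlaps counted once, within 0 to W, divided by W.

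For W = 120 minutes:

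| D (minutes) | 12 readings | 3 named times |
|---|---|---|
| 10 | 60/120 = 50% | 10/120 = 8% |
| 20 | 90/120 = 75% | 20/120 = 17% |
| 30 | 120/120 = 100% | 30/120 = 25% |

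For D = 20, the 12 readings cover onsets from 0 to 30, 40 to 60, 70 to 90 and 100 to 120 minutes, so 30 + 20 + 20 + 20 = 90. The three named times cover only 10 to 30, which is 20.

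**Step 5. Vary the assumptions.** The measure is the share of episodes touched by at least one of the 12 readings that touch none of the three named times: 1 − P(3 times)/P(12 readings). For D = 20 and W = 120 it is 1 − 0.167/0.75 = 78%.

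| D (minutes) | W | Share missed by the three times |
|---|---|---|
| 10 to 60 | 1 to 24 hours | 50% to 83% |
| 120 | 1 to 24 hours | 38% to 75% |
| 240 | up to 4 hours | 0% |
| 240 | 24 hours | 67% |

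The share is large for short episodes and falls to zero for 4-hour episodes that start within 4 hours.

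**The case against.** The strongest reply is that nothing is lost from the safety analysis as a whole. A reader might infer that most transient infusion reactions disappear, or that each dose will look better tolerated than the collected data show. The documents do not support either inference.

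- Section 15.3 reports all measurements at each time point, analyses safety at both individual and cohort level, and lists clinically significant vital-sign changes whenever they occur.
- Reactions recorded as AEs enter the cohort tables, for all grades and for grade 3 or higher, whatever their onset time.
- Section 5.1 defines a DLT over the continuous first 24 hours, so escalation does not depend on the three times.
- The general statement does not say that only cohort means will be shown, and in cohorts of 3 or 6 individual values can be read directly.

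All of that stands, and it limits the point to one summary.

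Two further replies stand in part. The times follow the mention of pulmonary function directly and may have been meant for spirometry alone; an AE is not something measured at 4 hours. If so, the sentence needs clarifying, and the count for vital signs then has no stated times at all. Also, the percentages in the working rest on assumed durations and onset, and treat scheduled readings as the only means of detection, although side effects are monitored throughout the 24 hours (Section 8.3.4). They describe this one count, not loss from the trial's safety data.

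What the reply does not supply is a number of affected subjects per dose, based on every scheduled reading.

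**Conclusion.** The point holds in a limited form. The acute-alteration summary applies the spirometry times to signs read at 12 post-infusion times. It omits 9 of the 12 readings, including 5 of the 7 in the first 4 hours. No any-reading count or per-subject worst value is specified, and neither the by-time summaries nor the listings stand in for one.

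The reading counts follow from the documents, taking nominal times and a last 4-hourly reading at 24 hours. The size of any under-count is not known: it depends on how long alterations last and when they begin, and the 50% to 83% range for episodes of 10 to 60 minutes is illustrative. DLT assessment, dose escalation, overall AE tables and listings are unaffected. The change is worth making because the summary concerns a component of the primary endpoint and the data are already being collected.

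**What to change.** Amend the acute summary in Section 15.3, or settle it in the detailed SAP that Section 15 says will be written before the final analysis.

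1. Keep 30 minutes, 4 hours and 24 hours for spirometry, and say that these times apply to spirometry only.
2. For vital signs and oxygen saturation, report by dose cohort the number and percentage of subjects with a clinically significant alteration at any scheduled reading from the infusion to 24 hours. For blood pressure, use the decreases already given in Section 15.3. That section gives no numeric criterion for saturation, temperature, heart rate or respiratory rate, so the SAP should state in advance how clinical significance is judged for these.
3. Add each subject's worst value for each sign, by dose cohort: lowest saturation, lowest systolic and diastolic pressure, and highest temperature, heart rate and respiratory rate.

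The cost is wording and one extra table, with no added procedures. The downside is that counting a crossing at any of 12 readings rather than 3 gives more room for chance crossings, so the table should be read beside the individual values.
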